10.1. Efficacy Measures

10.1.1. Primary Efficacy Measure

The primary efficacy measure is the change in HbA1c from baseline to 24 weeks.

10.1.2. Secondary Efficacy Measures

The following secondary efficacy measures will be considered for the comparison of other aspects of overall glycemic control:

- change in HbA1c from baseline to 6, 12, and 18 weeks or LOCF
- percentage of patients with HbA1c <7%, and the percentage of patients with HbA1c ≤6.5%
- 7-point SMBG measurements as listed in the Study Schedule ([Attachment 1](#))
 - premeal for each meal
 - postmeal for breakfast and lunch
 - bedtime
 - 3 am
- inpatient variability as measured by the standard deviation of the 7-point SMBG
- total insulin, basal insulin, and mealtime insulin lispro doses in U/day and U/kg/day
- weight change
- patient-reported outcomes as reflected in responses to ITSQ

10.2. Health Outcome/Quality of Life Measures

Self-reported patient questionnaires will be used to compare the health outcomes for the 2 insulins. This will be reflected in responses to ITSQ administered at baseline (Visit 2) and 24 weeks (Visit 13) or ED if a patient received at least one dose of study insulin.

The ITSQ is a validated instrument containing 22 items that assesses treatment satisfaction for patients with diabetes on insulin (Anderson et al. 2004). Items are measured on a 7-point scale, where lower scores reflect better outcomes. In addition to an overall score, the items that make up the 5 domains of satisfaction are categorized as:

- Inconvenience of Regimen (5 items)

- Lifestyle Flexibility (3 items)
- Glycemic Control (3 items)
- Hypoglycemic Control (5 items)
- Satisfaction with the Insulin Delivery Device (6 items)

All individual patient-domain scores will be calculated as the sum of the items in the domain. If an item score is missing for a patient and less than 20% of the items within the domain are missing for that patient, then the mean of all other patients' scores for that item will be imputed for the item. Otherwise, the domain score will be missing for the patient.

10.3. Safety Evaluations

Investigators are responsible for monitoring the safety of patients who have entered this study and for alerting Lilly or its designee to any event that seems unusual, even if this event may be considered an unanticipated benefit to the patient.

The investigator is responsible for the appropriate medical care of patients during the study.

The investigator remains responsible for following, through an appropriate health care option, AEs that are serious (SAEs), considered related to the study treatment or the study, or that caused the patient to discontinue before completing the study. The patient should be followed until the event is resolved or explained. Frequency of follow-up evaluation is left to the discretion of the investigator.

10.3.1. Adverse Events

Lilly has standards for reporting AEs that are to be followed regardless of applicable regulatory requirements that may be less stringent.

Lack of drug effect is not an AE in clinical studies because the purpose of the clinical study is to establish drug effect.

Study site personnel will record the occurrence and nature of each patient's preexisting conditions, including clinically significant signs and symptoms of the disease under treatment in the study.

After the ICF is signed, study-site personnel will record any change in the condition(s) and the occurrence and nature of any AEs. All AEs related to protocol procedures are reported to Lilly or designee.

In addition, all AEs, occurring after the patient receives the first dose of investigational product must be reported to Lilly or its designee via eCRF.

Any clinically significant findings from ECGs, labs, vital-sign measurements, or other procedures that result in a diagnosis should be reported to Lilly or its designee.

Investigators will be instructed to report to Lilly or its designee their assessment of the potential relatedness of each AE to protocol procedure, studied disease state, investigational product, and/or drug delivery system via eCRF.

The investigator decides whether he or she interprets the observed AEs as either related to disease, to the study medication, study procedure, or other concomitant treatment or pathologies. To assess the relationship of the AE to the investigational product, the following terminologies are defined:

- **Related:** a direct cause and effect relationship between the study treatment and the AE is likely
- **Unrelated:** without question, the AE is definitely not associated with the study treatment

If a patient's dosage is reduced or treatment is discontinued as a result of an AE, study site personnel must clearly report to Lilly or its designee via eCRF the circumstances and data leading to any such dosage reduction or discontinuation of treatment.

10.3.1.1. Serious Adverse Events

Serious adverse event collection begins after the patient has signed informed consent and received investigational product. If a patient experiences an SAE after signing informed consent, but prior to receiving investigational product, the event will NOT be reported as serious unless the investigator feels the event may have been caused by a protocol procedure.

Planned surgeries should not be reported as SAEs unless the underlying medical condition has worsened during the course of the study.

Study site personnel must alert Lilly or its designee of any SAE within 24 hours of investigator awareness of the event via a sponsor-approved method. If alerts issued via telephone, they are to be immediately followed with official notification on study-specific SAE forms. This 24-hour notification requirement refers to the initial SAE information and all follow-up SAE information.

An SAE is any AE from this study that results in one of the following outcomes:

- death
- initial or prolonged inpatient hospitalization
- a life-threatening experience (that is, immediate risk of dying)
- persistent or significant disability/incapacity
- congenital anomaly/birth defect
- considered significant by the investigator for any other reason.

Important medical events that may not result in death, be life-threatening, or require hospitalization may be considered serious adverse drug events when, based upon appropriate medical judgment, they may jeopardize the patient and may require medical or surgical intervention to prevent one of the outcomes listed in this definition.

For the purposes of this protocol, all episodes of severe hypoglycemia will be considered an SAE. If the investigator believes that a reported SAE of hypoglycemia does not fit any of the specific criteria outlined above (that is, death, initial or prolonged inpatient hospitalization, a life-threatening experience, persistent or significant disability/ incapacity, or congenital anomaly/birth defect), then the investigator should select “Other” as the outcome (that is, considered significant by the investigator for a reason other than those specified).

When a condition related to LY2963016 or Lantus® necessitates medical or surgical intervention to preclude either permanent impairment of a body function or permanent damage to a body structure, the serious outcome of “required intervention” will be assigned.

Serious adverse events occurring up to and including the patient’s last visit will be collected, regardless of the investigator’s opinion of causation, in the clinical data collection database and the pharmacovigilance system at the sponsor.

Pregnancy (during maternal or paternal exposure to investigational product) does not meet the definition of an AE. However, to fulfill regulatory requirements any pregnancy should be reported following the SAE process to collect data on the outcome for both mother and fetus.

Investigators are not obligated to actively seek AEs or SAEs in subjects once they have discontinued and/or completed the study (the patient summary CRF has been completed). However, if the investigator learns of any SAE, including a death, at any time after a subject has been discharged from the study, and he/she considers the event reasonably possibly related to the study treatment or study participation, the investigator must promptly notify Lilly.

Information on SAEs expected in the study population independent of drug exposure and that will be assessed by the sponsor in aggregate periodically during the course of the trial may be found in the IB.

10.3.1.1.1. Suspected Unexpected Serious Adverse Reactions

Suspected unexpected serious adverse reactions (SUSARs) are SAEs that are not listed in the IB and that the investigator identifies as related to the investigational product or procedure. Lilly has procedures for the recording and expedited reporting of SUSARs that are consistent with global regulatory regulations and detailed guidances and will be followed.

10.3.2. Other Safety Measures

Hypoglycemic events, vital signs, and weight will be collected as indicated in the Study Schedule ([Attachment 1](#)). Twelve-lead ECGs will be collected locally according to the Study Schedule ([Attachment 1](#)).

The ECG will be interpreted by a qualified physician (the investigator or qualified designee) at the site as soon after the time of ECG collection as possible, and ideally while the patient is still present, for immediate patient management and to determine whether the patient meets entry criteria.

10.3.3. Safety Monitoring

The Lilly CRP will monitor safety data throughout the course of the study.

Lilly will review SAEs within time frames mandated by company procedures. The Lilly CRP will, as is appropriate, consult with the functionally independent GPS therapeutic area physician or clinical scientist, and periodically review:

- trends in safety data
- laboratory analytes
- adverse events

If a study patient experiences elevated ALT or AST $\geq 3X$ ULN or elevated total bilirubin $\geq 2X$ ULN, clinical and laboratory monitoring should be initiated by the investigator. Details for hepatic monitoring depend upon the severity and persistence of observed laboratory test abnormalities. To ensure patient safety and comply with regulatory guidance, the investigator is to consult with the Lilly designated medical monitor regarding collection of specific recommended clinical information and follow-up laboratory tests. See [Attachment 2](#) and [Attachment 4](#).

10.3.4. Complaint Handling

Lilly collects product complaints on investigational products and drug delivery systems used in clinical studies in order to ensure the safety of study participants, monitor quality, and to facilitate process and product improvements.

The investigator or his/her designee is responsible for handling the following aspects of the product complaint process in accordance with the instructions provided for this study:

- recording a complete description of the product complaint reported and any associated AEs using the study-specific complaint forms provided for this purpose
- faxing the completed product complaint form within 24 hours to Lilly or its designee

If the investigator is asked to return the product for investigation, he/she will return a copy of the product complaint form with the product.

10.4. Sample Collection and Testing

[Attachment 1](#) lists the schedule for sample collections in this study.

[Attachment 2](#) lists the specific laboratory tests that will be performed for this study.

[Attachment 3](#) provides a summary of the estimated maximum number and volume of samples, for all sampling, during the study.

10.4.1. Samples for Study Qualification and Health Monitoring

Blood samples will be collected at the times specified in the Study Schedule ([Attachment 1](#)). Standard laboratory tests, including chemistry and hematology, will be performed. The clinical laboratory tests including a serum pregnancy test will be analyzed by a central laboratory. A

urine pregnancy test may be repeated locally for any visits if considered necessary by the investigators and/or in compliance with local regulations.

Investigators must document their review of each laboratory safety report.

Samples collected for specified laboratory tests will be destroyed within 60 days of receipt of confirmed test results. Tests are run and confirmed promptly whenever scientifically appropriate. When scientific circumstances warrant, however, it is acceptable to retain samples to batch the tests run, or to retain the samples until the end of the study to confirm that the results are valid. Certain samples may be retained for a longer period, if necessary, to comply with applicable laws, regulations, or laboratory certification standards.

10.4.2. Samples for Biomarker Research

10.4.2.1. Nonpharmacogenetic Biomarker Evaluations

This study will employ sample collection. Samples will be collected for nonpharmacogenetic biomarker investigation where local regulations allow. Fasting serum samples will be collected at the times specified in the Study Schedule ([Attachment 1](#)).

Fasting samples being collected will be used to measure C-peptide to support trial interpretation.

Samples will be coded with the patient number and may be stored for a maximum of 1 year following last patient visit for the trial at a facility selected by the Sponsor to enable further analysis of responses to the investigational products. The duration allows the Sponsor to respond to regulatory requests related to the investigational products.

10.4.3. Samples for Immunogenicity Research

Blood samples for immunogenicity testing will be collected to determine antibody production against LY2963016 or Lantus®. Immunogenicity will be assessed by a validated assay designed to detect antidrug antibodies in the presence of the investigational product. Antibodies may be further characterized and/or evaluated for their ability to neutralize the activity of the LY2963016 or Lantus®.

Samples may be stored for a maximum of 1 year following last patient visit for the trial at a facility selected by the sponsor to enable further analysis of immune responses to LY2963016 or Lantus®. The duration allows the sponsor to respond to regulatory requests related to the investigational product.

10.5. Appropriateness of Measurements

All efficacy and safety assessments included in this study are generally regarded as reliable and accurate with respect to diabetes mellitus.

11. Data Quality Assurance

To ensure accurate, complete, and reliable data, Lilly or its representatives will do the following:

- Provide instructional material to the study sites, as appropriate.
- Sponsor a start-up training session to instruct the investigators and study coordinators. This session will give instruction on the protocol, the completion of the CRFs, and study procedures.
- Make periodic visits to the study site.
- Be available for consultation and stay in contact with the study-site personnel by mail, telephone, and/or fax
- Review and evaluate CRF data and use standard computer edits to detect errors in data collection.
- Conduct a quality review of the database.

In addition, Lilly or its representatives will periodically check a sample of the patient data recorded against source documents at the study site. The study may be audited by Lilly or its representatives and/or regulatory agencies at any time. Investigators will be given notice before an audit occurs.

To ensure the safety of participants in the study, and to ensure accurate, complete, and reliable data, the investigator will keep records of laboratory tests, clinical notes, and patient medical records in the patient files as original source documents for the study. If requested, the investigator will provide the sponsor, applicable regulatory agencies, and applicable ERBs with direct access to original source documents.

11.1. Data Capture System

An electronic data capture system will be used in this study. The site maintains a separate source for the data entered by the site into the sponsor-provided electronic data capture system.

Case report form data will be encoded and stored in a clinical trial database. Data managed by a central vendor, such as laboratory test data, will be stored electronically in the central vendor's database system. Data will subsequently be transferred from the central vendor to the Lilly generic labs system.

Any data for which the paper documentation provided by the patient will serve as the source document will be identified and documented by each site in that site's study file. Paper documentation provided by the patient may include, for example, a paper diary to collect PRO measures (for example, a rating scale), a daily dosing schedule, or an event diary.

Data from study-specific product-complaint forms submitted to Lilly will be encoded and stored in the global product-complaint management system.

12. Sample Size and Statistical Methods

12.1. Determination of Sample Size

Based on the primary objective, to show noninferiority of LY2963016 to Lantus® at the 0.40% noninferiority margin (NIM), 109 completers per arm (218 total) are needed at 24 weeks. This calculation assumes no treatment difference in HbA1c between LY2963016 and Lantus®, a common standard deviation (SD) of 1.05% for change from baseline in HbA1c, a two-sided significance level of 0.05, and over 80% power. Assuming a 15% dropout rate at 24 weeks, the required number of randomized patients is 129 per arm (258 total).

Blinded sample-size reestimation may be performed when approximately 40% of the subjects have been enrolled in the study and finished 24-weeks of treatment, or about 6 months prior to the completion of enrollment, depending on which occur first by team assessment. This reestimation will use a statistical model to estimate the variability in the change in HbA1c from baseline to 24 weeks using all available patient HbA1c values at the time of data cutoff. The estimate of variability will then be used to recalculate the sample size that would be needed to have 80% conditional power for a NIM of 0.4%, assuming no difference between treatments. The sample size from the study is constrained by a predefined maximum sample size of 400 patients. If the recalculated sample size is smaller than sample size planned (258), the study will enroll to the sample size planned. If the recalculated sample size is larger than the planned sample size, the team will make a decision whether to increase sample size to the reestimated sample size. If the reestimated sample size is larger than the predefined maximum sample size, the team will increase the sample size to 400 subjects.

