5.1. Determination of Sample Size

5.1.1. Sample Size Section from the Protocol

Based on the primary objective, to show noninferiority of LY2963016 to Lantus® at the 0.40% noninferiority margin (NIM), 109 completers per arm (218 total) are needed at 24 weeks. This calculation assumes no treatment difference in HbA1c between LY2963016 and Lantus®, a common standard deviation (SD) of 1.05% for change from baseline in HbA1c, a two-sided significance level of 0.05, and over 80% power. Assuming a 15% dropout rate at 24 weeks, the required number of randomized patients is 129 per arm (258 total). This sample size is noted as the minimum sample size required in the study.

Blinded sample-size reestimation (bSSR) may be performed when approximately 40% of the subjects have been enrolled in the study and finished 24-weeks of treatment, or about 6 months prior to the completion of enrollment, depending on which occur first by team assessment. This reestimation will use a statistical model to estimate the variability in the change in HbA1c from baseline to 24 weeks using all available patient HbA1c values at the time of data cutoff. The estimate of variability will then be used to recalculate the sample size that would be needed to have 80% power for a NIM of 0.4%, assuming no difference between treatments. The sample size from the study is constrained between a predefined minimum sample size of 258, and a maximum sample size of 400 patients. If the recalculated sample size is smaller than minimum sample size planned, the study will enroll to the minimum sample size. If the recalculated sample size is larger than the planned minimum sample size, the team will make a decision whether to increase sample size to the reestimated sample size, bounded by the predefined maximum, or accept the consequent reduction in power.

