5.1.2. Blinded Sample Size Re-estimation

A bSSR procedure will be utilized to ensure that the trial has an appropriate sample size to achieve the pre-specified power. This procedure is blinded, in that it does not use information on treatment assignments. Only pooled data from a blinded snapshot will be used to estimate the variance of the primary endpoint. Based on the estimated variability, the final study size will be calculated. The allowable range of the final sample size is constrained in a pre-specified manner, subject to the planned and maximum sample size. The bSSR procedure described below was evaluated via simulation and is efficient in determining the appropriate sample size under a range of possible scenarios without inflating type 1 error. The methodology and implementation details are described below.

The bSSR procedure has four steps,

- 1) At a blinded snapshot, a Bayesian predictive model will use the available data to generate predictions (multiple imputations) of all future HbA_{1c} data yet to be observed in the trial using the available data at the snapshot (see Section 5.1.2.2).

- 2) These predicted datasets will each be analyzed using the primary analysis model. The residual errors from each model will be used to determine a predictive distribution of the total variability of change in HbA_{1c} from baseline to the end of the study.
- 3) The predictive distribution of the variability will be used to determine the recommended sample size.
- 4) The study team will consider the recommended sample size and decide on the final sample size.

For practical reasons, the final sample size is constrained by a pre-specified minimum, N_{\min} , and maximum, N_{\max} . Therefore if the estimated final sample size is greater than N_{\max} , 400 is recommended. If the estimated final sample size is less than N_{\min} , 258 is recommended. The resulting estimated sample size is a recommendation, is non-binding, but represents the model estimate of the appropriate sample size. The final decision on the sample size would be subject to constraints from the maximum and minimum sample sizes. Factors influencing the final sample size are described in Section 5.1.2.4.

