5.1.2.4. Determination of the Final Sample Size

The recommended sample size, \hat{N} , is non-binding, but the study team will use the recommendation when making the decision regarding the final sample size. The decision on the final sample size will consider the impact of the recommended sample size on two primary factors, 1) the feasibility of attaining the recommended sample size given the observed enrollment rate, and 2) the degree of certainty in the recommended sample size. Regardless of this decision process, the final target sample size will be no smaller than approximately N_{\min} (258 for this study) and no larger than approximately N_{\max} (400 for this study).

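### For a blinded re-estimate above 400, the protocol requires 400 patients while the SAP makes 400 optional and lets the team stay at 258

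*Protocol*

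**What the plan says.** Protocol 12.1 makes the blinded re-estimation optional and gives three branches. Below 258, the trial enrols 258. Above 258, the team decides whether to increase. Above the maximum there is no option: "If the reestimated sample size is larger than the predefined maximum sample size, the team will increase the sample size to 400 subjects". The stated target is 80% conditional power.

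SAP 5.1.1 carries the heading Sample Size Section from the Protocol, but the third branch is absent. For any re-estimate above the minimum, the team may increase, "bounded by the predefined maximum, or accept the consequent reduction in power". The target here is 80% power.

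SAP 5.1.2 introduces the procedure more firmly: "A bSSR procedure will be utilized to ensure that the trial has an appropriate sample size to achieve the pre-specified power". The same section then says that a result above the maximum leads only to a recommendation of 400, and that the recommendation does not bind. SAP 5.1.2.4 repeats this: "the study team will use the recommendation when making the decision regarding the final sample size". It names feasibility and the certainty of the recommendation as the deciding factors, and limits the final target only to roughly 258 to 400.

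The formula parameters in SAP 5.1.2.1 and 5.1.2.3 are one-sided alpha 0.025, beta 0.05, difference 0, margin 0.4% and dropout 15%. A beta of 0.05 means 95% power, not 80%.

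**The concern.** If the blinded re-estimate comes out above 400, staying at 258 follows the SAP and breaches the protocol. The SAP sections do not mark the change, and the heading of 5.1.1 suggests that nothing has changed. The sponsor would then have to decide which document governs after seeing the blinded SD.

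What is at stake is the final sample size, and so the power of the primary non-inferiority comparison. SAP 5.1.2 also tells the reader that the procedure secures the planned power, which an optional, non-binding and capped procedure cannot do.

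**Working it through.** **Inputs (Protocol 12.1, repeated in SAP 5.1.1).** Margin and completers: "at the 0.40% noninferiority margin (NIM), 109 completers per arm (218 total) are needed at 24 weeks". Difference: "This calculation assumes no treatment difference in HbA1c between LY2963016 and Lantus". SD: "a common standard deviation (SD) of 1.05% for change from baseline in HbA1c". Error rates: "a two-sided significance level of 0.05, and over 80% power". Dropout is 15%, the minimum N is 258 and the maximum is 400.

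**Step 1: reproduce the planned figure.** Completers per arm = 2(1.96 + 0.8416)² × 1.05² / 0.4² = 108.2, rounded up to 109. Then 109/0.85 = 128.2, rounded up to 129 per arm, or 258 in total. Power with 109 per arm is 80.3%. The plan's figure reproduces.

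**Step 2: where the disputed branch starts.** The SAP formula is N = 4(z₀.₉₇₅ + z_power)² SD² / 0.4² / 0.85. Setting N = 400 gives SD = √(400 × 0.85 × 0.16 / 4) / (z₀.₉₇₅ + z_power) = 3.688 / (z₀.₉₇₅ + z_power).

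- 80% target: 3.688 / 2.8016 = 1.316.
- 95% target (printed beta 0.05): 3.688 / 3.6049 = 1.023.

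**Step 3: power at the two sample sizes.** Power = Φ(0.4 / (SD√(2/n)) − 1.96), with n = 0.85N/2 completers per arm. That is 170 at N = 400 and 109.65 at N = 258.

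| SD | Re-estimate, 80% target | Re-estimate, beta 0.05 | Power at 400 | Power at 258 |
|---|---|---|---|---|
| 1.05 | 255 | 421 | 94.0% | 80.5% |
| 1.316 | 400 | 662 | 80.0% | 61.4% |
| 1.4 | 452 | 749 | 75.0% | 56.2% |
| 1.5 | 519 | 860 | 69.1% | 50.6% |

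Example at SD 1.4 with N = 400: 0.4 / (1.4 × √(2/170)) − 1.96 = 2.634 − 1.96 = 0.674, and Φ(0.674) = 75.0%.

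**Step 4: read the table against the rules.** At the 80% target, the documents disagree only beyond SD 1.316, so the last two rows measure the conflict. The 1.316 row is the limiting value at the threshold. With the printed beta of 0.05, every row has a re-estimate above 400, including the planned SD: the protocol would require 400 and the SAP would permit 258. The 258 column is the SAP's extreme; the team could also choose a number in between.

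**Step 5: test the claim in SAP 5.1.2.** Under the SAP, the team may stay at 258 whatever SD is found. Under the protocol, the re-estimation may be skipped, the increase is optional between 258 and 400, and above that 400 gives less than 80% (75.0% at SD 1.4). Neither rule secures 80%.

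**The case against.** The strongest reply is that this is a narrow mismatch in a legitimate design. A blinded, bounded, non-binding re-estimation is a reasonable sponsor choice, SAP 5.1.1 openly admits the possible loss of power, and SAP 5.1.2.4 names the factors that will decide. That stands: the SAP rule is not unsound in itself. The problem is that it differs from the protocol's rule while being presented as the protocol's.

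A reader might infer that the SAP turns a generally binding protocol rule into a free choice, with 80% against 61% power as the cost. The documents do not support that. The protocol already leaves re-estimates from 258 to 400 to the team, so at SD 1.2 (re-estimate about 333) the 69% power at 258 is a choice that the protocol itself allows. The 80% and 61% pair belongs to the threshold; beyond it, both figures are lower.

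It could also be argued that a re-estimate above 400 is also above 258, so the protocol's discretionary sentence covers it and the last sentence merely caps the number. But Protocol 12.1 has already stated the maximum, and the last sentence is specific and offers no option. The plain reading is that it governs.

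An SD above 1.316 is at least 25% above plan (1.316/1.05 = 1.25), and nothing in the documents shows it to be likely. That is fair at the 80% target. It fails if the formula is run with its printed beta, because the planned SD is then enough.

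Finally, a reader might suspect bias because the trial is open label. The documents do not support this: the snapshot carries no treatment assignment (SAP 5.1.2.2), the study team's review of summary data stays blinded until final lock (SAP section 6), and SAP 5.1.2 reports simulations without type I error inflation.

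**Conclusion.** The conflict is real and confined to re-estimates above 400, where the protocol mandates 400 and the SAP does not. At the 80% target it begins at SD 1.316, and the power at stake is about 18 to 19 percentage points (75.0% against 56.2% at SD 1.4; 69.1% against 50.6% at SD 1.5). With the printed beta of 0.05 it begins at SD 1.023 and includes the planned SD, where the choice is between about 94% and 80%. Which range applies cannot be settled until the beta is reconciled with the 80% in the text. Separately, the assurance of power in SAP 5.1.2 does not hold under either rule.

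The figures assume zero true difference, 15% dropout, a completers-only comparison and the normal approximation. The noncentral t changes them little (79.8% and 60.8% at SD 1.316). The point concerns power and pre-specification only.

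**What to change.** 1. Reconcile the beta of 0.05 in SAP 5.1.2.1 and 5.1.2.3 with the 80% target in Protocol 12.1 and SAP 5.1.1, since it decides when the disputed branch is reached.
2. State one rule for re-estimates above 400 in both documents. Either restore the protocol's rule in SAP 5.1.1 and 5.1.2.4, with matching wording in 5.1.2 (a re-estimate above 400 means a target of 400), or amend Protocol 12.1 to the non-binding rule.
3. In either case, replace the opening claim of SAP 5.1.2 with wording to this effect: *the procedure informs the final sample size; because it is optional and capped, and an increase may be declined, power may be below 80%*. If the protocol's rule is restored, limit the reference to declining an increase to re-estimates from 258 to 400.
4. In Protocol 12.1, write *power* rather than *conditional power*. The calculation uses a blinded variance and an assumed zero difference, and does not condition on an observed treatment effect.

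The cost is SAP wording and a short protocol clarification or amendment. The ceiling of 400 is already in both documents, so no new maximum is created. The downside is less discretion for the team under the first option, or a less favourable stated power under the second.
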